Treatment policy strategy is defined as the strategy that considers "The occurrence of the intercurrent event is irrelevant: the value for the variable of interest is used regardless of whether or not the intercurrent event occurs." (per ICH E9 R1 Addendum). Intercurrent events can include but are not limited to the following: (1) discontinuation of study drug, (2) discontinuation of the study, or (3) initiation of a new treatment. In a situation that missingness of the eGFR or LVMI data cannot be predicted solely based on subject's observed data, such missingness will not be considered as missing at random, but rather as MNAR. The missing pattern will be evaluated and subjects with and without missing data will be compared to gain understanding of the nature of the missingness. Pattern-mixture models and Monte Carlo Markov Chain methodology will be implemented in

multiple imputation with a list of observed variables and covariates to impute missing eGFR and LVMI data with the assumption of MNAR. The covariates can be variables related to missingness identified in the comparison of subjects with and without missing data, the covariate can also be variables related to eGFR or LVMI based on medical input.

The analyses of the primary endpoints will be performed with all available data through Week 104. The repeated measure analyses will be based on the restricted maximum likelihood method assuming an unstructured covariance matrix to model the within-subject errors. If the analysis fails to converge, a compound symmetry covariance structure will be used to model the within-subject errors. Denominator degrees of freedom for the F test for fixed effects will be estimated using the Kenward-Roger approximation.

The following analyses will be performed for the primary endpoints to evaluate the robustness of the results from the primary analysis methods:

- MMRM analysis using the completers set
- MMRM analysis using the PP set.
- The eGFR and LVMI annualized rate of change and 95% CI will be estimated for subjects using the random intercept and slope model. Baseline eGFR or baseline LVMI, age at baseline, sex, and treatment duration on investigational product in year will be included in the model.
- Tipping point analysis with multiple imputation approach in ITT and mITT sets.

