^v The following medications and treatments are prohibited at any time prior and throughout the course of the study: FABRAZYME[®] (agalsidase beta) and its biosimilars, GLYSET[®] (miglitol), ZAVESCA[®] (miglustat), CERDELGA[®] (eliglustat), GALAFOLD[®] (migalastat), and any investigational product for treatment of Fabry disease. Treatment at any time during the study with the following medications is prohibited: Chloroquine, Amiodarone, Monobenzone, and Gentamicin.

17 Feb 2022

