7.2 Withdrawal from the Study

A subject may withdraw from the study at any time and for any reason, without prejudice to his/her future medical care by the physician or at the institution, or may be withdrawn at any time at the discretion of the investigator or sponsor (eg, in the interest of subject safety). The investigator is encouraged to discuss withdrawal of a subject with the medical monitor when possible. Withdrawal from the study means that the subject is no longer taking study treatment and does not return for further study visits. A subject who is withdrawn from the study does not meet the criteria to be part of the "completer set" for statistical analysis.

The investigator should make a reasonable effort to ascertain the reason(s) for withdrawal, while fully respecting the subject's right to do so. The reason for withdrawal should be recorded in the subject's source documentation. If a subject is withdrawn for more than 1 reason, each reason should be documented in the source documentation and the most clinically relevant reason should be indicated.

Reasons for withdrawal from the study may include, but are not limited to:

- Adverse event
- Protocol deviation
- Withdrawal by subject
- Lost to follow-up
- Lack of efficacy
- Death
- Pregnancy

Subjects wishing to completely withdraw from the study should be encouraged to complete the Week 104 (end of treatment or early termination visit) and safety follow-up assessments to ensure subject safety. Comments (spontaneous or elicited) or complaints made by the subject must be recorded in the source documents. The reason for withdrawal, date of stopping

Shire SHP675-301 Protocol Amendment 6 REPLAGAL[®] (agalsidase alfa)

investigational product, and the total amount of investigational product taken must be recorded in the source documents.

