The primary analysis for change from baseline at Week 104 in LVMI will be based on a MMRM with multiple imputation under the assumption that missing is not at random (MNAR) using the ITT population. The primary null hypothesis to be tested for LVMI is that the mean change from baseline in LVMI at Week 104 of treated subjects is greater than or equal to $10 \text{ g/m}^{2.7}$, the mean change of the reference untreated subjects. The alternative hypothesis is that the mean change in LVMI is less than $10 \text{ g/m}^{2.7}$, the reference value of untreated subjects. A one-sided p-value to test if the mean change is less than $10 \text{ g/m}^{2.7}$ from MMRM model will be used to interpret that there is sufficient evidence to reject the null hypothesis. The model will include visit as the fixed effect; with adjustment for sex (male versus female), age at baseline and baseline LVMI. In the model, visit will be treated as a class variable, assuming an unstructured covariance matrix to model the within subject variability.

Missing eGFR and LVMI data due to intercurrent event or other reasons will be handled according to the treatment policy strategy. Treatment policy strategy is defined as the strategy that considers "The occurrence of the intercurrent event is irrelevant: the value for the variable of interest is used regardless of whether or not the intercurrent event occurs." (per ICH E9 R1 Addendum). Intercurrent events can include but are not limited to the following: (1) discontinuation of study drug, (2) discontinuation of the study, or (3) initiation of a new treatment. In a situation that missingness of the eGFR or LVMI data cannot be predicted solely based on subject's observed data, such missingness will not be considered as missing at random, but rather as MNAR. The missing pattern will be evaluated and subjects with and without missing data will be compared to gain understanding of the nature of the missingness. Pattern-mixture models and Monte Carlo Markov Chain methodology will be implemented in multiple imputation with a list of observed variables and covariates to impute missing eGFR and LVMI data with the assumption of MNAR. The covariates can be variables related to missingness identified in the comparison of subjects with and without missing data, the covariate can also be variables related to eGFR or LVMI based on medical input.

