The analyses of the primary endpoints will be performed with all available data through Week 104. The repeated measure analyses will be based on the restricted maximum likelihood method assuming an unstructured covariance matrix to model the within-subject errors. If the analysis fails to converge, a compound symmetry covariance structure will be used to model the within-subject errors. Denominator degrees of freedom for the F test for fixed effects will be estimated using the Kenward-Roger approximation.

The following analyses will be performed for the primary endpoints to evaluate the robustness of the results from the primary analysis methods:

- MMRM analyses using the completers set
- MMRM using the PP set
- The eGFR and LVMI annualized rate of change and 95% CI will be estimated for subjects using the random intercept and slope model. Baseline eGFR or baseline

LVMI, age at baseline, sex, and treatment duration on investigational product in year will be included in the model.

Tipping point analysis with multiple imputation approach will be conducted for • analyses of change from baseline in eGFR or LVMI at week 104 in ITT.

Descriptive summary statistics including the number of subjects (n) and mean (standard deviation [SD]) of raw values of each the primary endpoints and change from baseline at each visit will be presented by visit. The analysis of efficacy endpoints should be based primarily on the ITT and mITT sets, and subsequently on completers and PP sets.

Descriptive summary statistics for each of the primary endpoints will also be provided by sex subgroups.

9.5.2 **Secondary Efficacy Endpoints**

nercial use only The same model used for the primary endpoints will be used. The secondary efficacy endpoints are:

- Annualized rate of change in eGFR
- Annualized rate of change in LVMI
- Change over time in eGFR
- Change over time in LVMI •
- Change over time in proteinuria, measured by PCR
- Change over time of the number of fibrotic segments suggestive of cardiac fibrosis as assessed by volume of fibrosis, measured by cMRI
- Change over time in IVSTd and PWTd, measured by cMRI •
- Change over time in plasma lyso-Gb3.

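### eGFR and LVMI values observed after a switch to another Fabry therapy would count towards REPLAGAL's result, and the planned completers check does not reliably remove them

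*Combined protocol and SAP*

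**What the plan says.** Section 9.5.1 (and the Synopsis, in the same terms) states: "Missing eGFR and LVMI data due to intercurrent event or other reasons will be handled according to the treatment policy strategy". It takes treatment policy to mean that "the value for the variable of interest is used regardless of whether or not the intercurrent event occurs". The list of events is open: "Intercurrent events can include but are not limited to the following", followed by "1) discontinuation of study drug, (2) discontinuation of the study, or (3) initiation of a new treatment". A new treatment is not defined anywhere in the documents. The same section adds: "The analyses of the primary endpoints will be performed with all available data through Week 104".

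The primary analysis is in the ITT set. It tests the mean Week 104 change against fixed untreated values of -6 mL/min/1.73 m² (eGFR) and +10 g/m^2.7 (LVMI), with no concurrent arm (Sections 4.1 and 9.5.1).

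On conduct, Section 6.6.3 and footnote v of Table 1 list other Fabry therapies under the rule: "The following medications and treatments are prohibited at any time prior and throughout the course of the study". Section 7.2 names protocol deviation among possible grounds for leaving the study, but its wording is permissive: "Reasons for withdrawal from the study may include, but are not limited to". Section 7.3 lets subjects who stop REPLAGAL continue site visits and encourages them to do so through Week 104. No section says what happens to eGFR or LVMI values recorded after a prohibited Fabry therapy is started.

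**The concern.** Section 2.3 gives the study's purpose as confirming the efficacy of REPLAGAL. In a randomised trial, treatment policy values after a switch still have a comparator measured under the same policy. Here the comparator is a constant taken from patients who stayed untreated for two years. If a subject stops REPLAGAL, starts another effective Fabry therapy and is measured at Week 104, any benefit of that therapy moves the mean towards rejection. Nothing in the design separates it from a REPLAGAL effect.

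The planned robustness analyses would be expected to expose this. They do so only in part, as set out in the working. Stopping REPLAGAL with no replacement does not create the problem.

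**Working it through.** **Inputs.** Section 9.3: 45 enrolled, 36 evaluable; one-sided 0.0125 per endpoint; SD 7 (eGFR) and 15 (LVMI); planned Week 104 changes of -1.7 and +0.64 against references of -6 and +10. Planned differences: 6 - 1.7 = 4.3 and 10 - 0.64 = 9.36.

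**1. The plan's own figure.** Effect sizes are 4.3/7 = 0.614 and 9.36/15 = 0.624. With n = 36 the noncentrality parameters are 0.614 × √36 = 3.69 and 3.74. Exact one-sample t-test power is 90.5% and 91.4%, so the stated power of at least 90% is reproduced. 36/(1 - 0.20) = 45, also as stated.

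**2. Effect of switchers.** The documents give no switch rate, so a range is shown. Assumptions: REPLAGAL has no effect; 45 subjects have Week 104 values; k of them switch; the new therapy's benefit accrues in proportion to time on it, at the rate planned for REPLAGAL. The share gained is h = (104 - week of switch)/104, so Week 78 gives 26/104 = 0.25 and Week 52 gives 0.5.

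Shift of the mean = (k/45) × h × planned difference. For eGFR with k = 2 and h = 0.5 this is (2/45) × 0.5 × 4.3 = 0.096. The standard error is 7/√45 = 1.04, so the shift is 0.09 standard errors.

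Rejection probability by simulation (one-sample t-test standing in for the MMRM, 1,000,000 replicates; a repeat with 400,000 agreed within 0.05 percentage points). The last column treats the endpoints as independent: 1 - (1 - p₁)(1 - p₂).

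| Switchers | eGFR, h = 0.25 / 0.5 | LVMI, h = 0.25 / 0.5 | At least one false success |
|---|---|---|---|
| nominal | 1.25% | 1.25% | 2.5% |
| 1 | 1.33 / 1.39% | 1.31 / 1.39% | 2.6-2.8% |
| 2 | 1.41 / 1.56% | 1.42 / 1.56% | 2.8-3.1% |
| 5 | 1.65 / 2.12% | 1.65 / 2.15% | 3.3-4.3% |
| 9 (upper bound) | 2.02 / 3.18% | 2.06 / 3.18% | 4.0-6.3% |

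Nine is 20% of 45: every anticipated non-completer would have to switch, stay and be measured at Week 104.

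**3. Do the robustness analyses catch it?**

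- Completers set: the Synopsis (number of subjects and sample size justification) ties this set to subjects still on investigational product with both primary endpoints at baseline and Week 104. Section 9.3 uses the same evaluability rule, and Section 7.3 says subjects who stop treatment and complete visits are not completers. The formal definitions, in the Synopsis under subject populations and in Section 9.4, require only the valid values. Under the formal wording a measured switcher stays in.
- Per-protocol set: drops a switcher only if the switch is classed as a major deviation, and major deviations are not listed.
- Random intercept and slope model: includes "treatment duration on investigational product in year" as a covariate but keeps post-switch values.
- Tipping-point analysis: varies imputed values, not observed ones.

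**4. Which replacement for post-switch values?** Lack of efficacy is a listed reason for stopping treatment (Section 7.3), so switchers may be faster progressors. Suppose that, without switching, they would have declined 0.5 SD (3.5 mL/min/1.73 m²) more than the overall mean of -6. Imputing them like the remaining subjects then amounts, approximately, to analysing the other 45 - k, whose mean lies 3.5k/(45 - k) above -6: 0.16, 0.44 and 0.88 for k = 2, 5 and 9. Exact t-test error is about 1.8%, 3.2% and 6.4%. Keeping the observed values in the same scenario gives about 1.4-1.5%, 1.6-2.1% and 1.9-3.2%. That form of imputation can be worse than the problem.

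Imputing at the untreated rates does not borrow from the remaining subjects. In simulation (50 imputations, Rubin's rules, 40,000 replicates, switchers otherwise like the rest), null error with 2 and 5 switchers was 0.99% and 0.51% for eGFR, and 0.95% and 0.58% for LVMI.

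**The case against.** The strongest reply is that the situation will hardly arise. Other Fabry therapies are prohibited, a breach can lead to withdrawal, and after withdrawal later values are missing rather than observed. With one or two switchers, error stays within about 0.3 percentage points of nominal, and even that assumes REPLAGAL does nothing and the new drug works at the full planned rate. This stands, and it sets the size of the point. It does not remove it: a prohibition is not a data rule, withdrawal is optional, and the plan itself names the event.

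Second, the governing sentence speaks of missing data, so it might not be meant for observed values. That is a fair reading of one sentence. The quoted definition and the use of all available data point the other way, so at the least the wording is unclear.

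Third, treatment policy is a recognised strategy, openly stated, and a separate SAP is announced (Section 9.1) that may settle the matter. Both are true. That SAP is not among the documents reviewed.

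**Conclusion.** The point holds as a modest gap in the handling of one intercurrent event, together with a plain inconsistency in the completers definition. Under the stated assumptions, per-endpoint error rises from 1.25% to about 1.3-1.6% with one or two switchers and 1.7-2.1% with five. The number of switchers cannot be known in advance, and the power calculation is unaffected.

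A reader might infer more, and the documents do not support it:

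- That switching is likely to produce a spurious success. The prohibition makes more than a few switchers improbable, and the nine-switcher row is a bound, not a forecast.
- That treatment policy must be replaced in the primary analysis, or an efficacy claim barred if it depends on post-switch values. Neither follows from an effect of this size. A sensitivity result reported beside the primary one lets readers judge.
- That follow-up after stopping REPLAGAL is itself a flaw. Without a replacement therapy those values raise no such difficulty, and collecting them is sound.

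**What to change.** 1. In Section 9.5.1 and the Synopsis, define a new treatment as any other treatment specific to Fabry disease, in the sense of inclusion criterion 7, and reconcile this with the list in Section 6.6.3. Keep treatment policy for stopping study drug without replacement, and say explicitly that the rule concerns observed values, separately from the handling of missing ones.
2. Prespecify one sensitivity analysis of both primary endpoints. Set values after the start of such a therapy to missing and impute them from the time of the switch at the untreated rates in Section 4.2 (-3 mL/min/1.73 m² and +5 g/m^2.7 per year). Report it beside the as-observed primary result, with the number and timing of switchers. Do not impute switchers like the remaining subjects.
3. Add the condition of not having stopped investigational product to the completers definition in the Synopsis (subject populations) and Section 9.4, to match Sections 7.3 and 9.3.

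Cost: wording and a little analysis work, since concomitant medications and visit data are already collected. There is no effect if nobody switches. If REPLAGAL works as planned and subjects switch between Week 52 and Week 78, simulated power of the sensitivity analysis with 2 and 5 switchers is about 95% and 93-94% for eGFR (96% with none), and 96% and 94-95% for LVMI (97% with none). No change to patient care is involved. If the separate SAP already contains these rules, only the protocol text needs aligning.

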9.5.3 Multiplicity Adjustment

The following strategies will be employed to alleviate the issue of multiple testing in this study:

- Defining several primary endpoints creates a multiplicity problem. Testing each endpoint separately at α =0.05 would inflate the Type I error and overstate the statistical significance. Therefore, failure to account for multiplicity can lead to false inference regarding the effects of a drug. To address the multiplicity problem, a Bonferroni adjustment will be implemented.
- Apart from the two primary endpoints, all other endpoints will be considered to be secondary, and any significant finding amongst these outcomes will not therefore be interpreted as confirmatory.
- Prespecification of analysis populations, subgroups of interest, methods for calculating and analyzing each outcome, would reduce the potential for multiplicity. To this end, all these issues will be described and documented in the SAP prior to any statistical analysis.

9.5.4 Control of Type I Error

A Bonferroni adjustment will be used to control the overall one-sided type I error rate.

9.5.5 Exploratory Efficacy Endpoints

The exploratory efficacy endpoint is the change over time in serum levels of inflammatory biomarkers including but not limited to INTLK1 β , TNF- α , VCAM1, and ICAM1.

Concentrations of inflammatory biomarkers will be summarized using descriptive statistics: mean, SD, median, first and third quartiles, minimum and maximum. Initially, simple summary statistics will be produced for each inflammatory biomarker. Subsequently, MMRM will be performed to explore the changes of INTLK1 β , TNF- α , VCAM1, and ICAM1 over the course of follow-up. MMRM will be calculated using unstructured covariance (subject level) and REML. The MMRM will include the fixed effect of visit. Significance tests will be based on least-squares means. Further on, if considered necessary, the MMRM will be repeated for each inflammatory biomarker to account for any prespecified possible baseline confounder.

All analyses related to inflammatory biomarkers will be performed using the ITT and mITT sets.

9.6 Safety Analyses

The safety endpoints include:

- AEs
- ADA assessments, including NAbs for samples confirmed positive for ADA
- Clinical laboratory tests (serum chemistry, hematology, and urinalysis)
- Electrocardiography
- Vital signs.

Shire SHP675-301 Protocol Amendment 6 **REPLAGAL**[®] (agalsidase alfa)

17 Feb 2022

All safety analyses will be presented for the safety set. All safety measures including, vital signs, clinical laboratory results (hematology, chemistry, urinalysis), ECG, and ADA (including NAbs) assessments will be summarized descriptively at baseline and for each postbaseline visit. Shift from baseline will be provided, if applicable.

Treatment emergent adverse events (TEAEs) are defined as AEs that start or deteriorate during or after the first dose of investigational product through the safety follow up visit/contact. The number of events, incidence, and percentage of TEAEs will be calculated overall and by system organ class and preferred term at both subject level and adverse event level. TEAEs will be further summarized by severity and relationship to investigational product. Multiple events of the same type will be combined for each subject and, when doing this, the worst severity or outcome for each event type will be presented for the analysis. When calculating event rates, the denominator will be the number of subjects commencing follow-up in the relevant analysis population, irrespective of dropouts during the course of follow-up. Adverse events related to investigational product including IRRs, AEs leading to withdrawal, SAEs, and deaths will be similarly summarized/listed.

9.7 **Other Analyses**

9.7.1 Health-related Quality of Life Analyses

USE ONLY The change over time in subject rating of pain, fatigue, severity of global Fabry symptoms and -idp quality of life will be analyzed as exploratory endpoints using the following PRO measures, respectively:

- SF-36v2 0
- BPI-SF 0
- PGI-S 0
- BFI 0
- GSRS 0

Initially, simple summary statistics will be produced for the overall score and (if available) any subscale score of each PRO measure. Continuous variables will be summarized using the following descriptive statistics: mean, SD, median, first and third quartiles, minimum and maximum. The number and percentage of observed levels will be reported for all categorical measures. Subsequently, MMRM will be performed to explore the changes of PRO measures over the course of follow-up. MMRM will be calculated using unstructured covariance (subject level) and REML. The MMRM will include the fixed effect of visit. Significance tests will be based on least-squares means. Further on, if considered necessary, the MMRM will be repeated for each PRO measure to account for any prespecified possible baseline confounder.

All analyses related to PRO measures will be performed using the ITT and mITT set.

